**Primary Safety Endpoints:**

1. Cumulative incidence of grade 3 and 4 adverse events during the study period
2. Cumulative incidence of serious adverse events during the study period

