#### 2.1.2. Primary Safety Objective:

To evaluate the safety of anti- SARS-CoV-2 plasma versus control (albumin 5%)

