## 3.2 Statistical Analysis

Primary Analysis and go/no-go decision: The severity scale of the two groups will be compared using stratified, Mann Whitney test. Specifically, a one-sided  $P < 0.15$  favoring the immune plasma arm will constitute a “go decision” in this phase 2 trial, suggesting evidence of promise for further investigation in an expanded Phase 3 study. The results in this trial will then be used to plan the Phase 3 sample size, with possibility that the data in this Phase 2 trial will be included in the final analysis using adjusted  $P$  values. Details of sample size re-estimation and adjusted analysis, as well as the final statistical analysis plan, will be determined before unblinding the study data.

This analysis will be intent-to-treat. Given the short study duration and the nature of the treatment, however, we anticipate minimal non-compliance and loss to follow-up.

Subgroup Analysis: If the stratified analysis reaches the go decision, with  $P < 0.15$ , we will explore the treatment effect within each stratum using Mann Whitney test.

Secondary Analyses: All secondary efficacy analyses will be intent-to-treat. Time-to-event variables (e.g. time to death) will be analyzed using Cox proportional hazard model. Longitudinal data collected over multiple days (e.g., PCR positivity) will be analyzed using generalized linear mixed models. Treatment effects on these variables will be estimated with 95% confidence intervals.

Safety Analyses: Serious adverse events will be summarized by grades and types using proportions and 95% confidence intervals for the two study arms, and the two arms will be compared using Fisher's exact test.

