## 6.6 Safety monitoring

1. Safety evaluations will assess for the safety of anti-SARS-CoV-2 plasma and determine if risks are higher, lower or the same as control (albumin 5%)
2. Clinical evaluations: Vital signs and symptom screen on days -1, 0, 3, 7, 14 and symptom screens on days 1, 28 and 60. Parameters requiring referral for urgent medical care are included in each evaluation
3. Safety laboratory tests, including ABO blood type (day -1) pregnancy testing (day -1), CBC and comprehensive metabolic panel (days -1, 7 and 14), will be performed at the local CLIA-certified clinical laboratory

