## 6.7 Adverse Event Reporting

An **Adverse Event (AE)** is any untoward or unfavorable medical occurrence in a human subject, including any abnormal sign, symptom or disease, temporally associated with the subject's participation in research, whether or not considered related to the subject's participation in the research.

**Serious Adverse Event (SAE):** any adverse event temporarily associated with the subject's participation in research that meets any of the following criteria:

- Results in death;
- Is life-threatening (places the subject at immediate risk of death from the event as it occurred);
- Requires inpatient hospitalization or prolongation of existing hospitalization;
- Results in a persistent or significant disability/incapacity;
- Results in a congenital anomaly/birth defect; or
- Any other adverse event that, based upon appropriate medical judgment, may jeopardize the subjects' health and may require medical or surgical intervention to prevent one of the other outcomes listed in this definition.

An **Unanticipated Problem (UP)** is any incident, experience or outcome involving risk to subjects or others in any human subjects research that meets all of the following criteria:

- Unexpected (in terms of nature, severity or frequency) given (a) the research procedures that are described in the IRB-approval protocol and informed consent document, and (b) the characteristics of the subject population being studied;
- Related or possibly related to participation in such research (i.e., there is a reasonable possibility that the incident, experience or outcome may have been caused by the procedures involved in such research); and
- Suggests that the research places subjects or others at a greater risk of harm (including physical, psychological, economic or social harm) than was previously known or recognized

A **Suspected Adverse Reaction (SAR)** is any AE for which there is a reasonable possibility that it was caused by the drug.

Reasonable possibility means that there is evidence to suggest a causal relationship between the drug and the AE. Examples of reasonable possibility are:

- A single occurrence of an event that is uncommon and known to be strongly associated with drug exposure.
- One or more occurrences of an event that is not commonly associated with drug exposure, but is otherwise uncommon in the population exposed to the drug.

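### The safety analysis gives no interval for the between-arm difference, and its SAE comparison, if pooled, mixes product harm with COVID-19 outcomes that the efficacy scale already counts

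*Combined protocol and SAP*

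**What the plan says.** The formal safety objective (Section 2.1.2) is a comparison with albumin and goes no further than evaluation: "To evaluate the safety of anti- SARS-CoV-2 plasma versus control (albumin 5"%). Section 6.6 goes further and says the evaluations will "determine if risks are higher, lower or the same as control (albumin 5"%).

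The Protocol Summary lists two primary safety endpoints: "Cumulative incidence of grade 3 and 4 adverse events during the study period" and "Cumulative incidence of serious adverse events during the study period".

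For analysis, Section 3.2 says "Serious adverse events will be summarized by grades and types using proportions and 95% confidence intervals for the two study arms", and that "the two arms will be compared using Fisher's exact test". It names no level, sidedness or unit for that test (the SAE total, or each type), no interval for the difference and no margin. It gives no analysis of the grade 3 and 4 endpoint. The preceding paragraph of the same section does promise treatment effects with 95% confidence intervals for the secondary efficacy variables.

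Section 6.7 defines an SAE to include any event that "Results in death" or "Requires inpatient hospitalization or prolongation of existing hospitalization". It makes no exception for progression of COVID-19.

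**The concern.** There are two separate problems.

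**The method does not answer the question in Section 6.6.** Intervals for each arm and a P value do not estimate the difference in risk. With 50 controls a non-significant Fisher test is compatible with a large excess of harm, and without a margin no result could show that risks are the same.

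**The SAE endpoint overlaps the efficacy endpoint.** Every participant has COVID-19. Admission, ICU care and death are categories 4-7 of the severity scale, and new admissions and deaths also count as SAEs. If plasma works, it lowers the SAE total, and that reduction is set against any SAEs the product causes. A pooled comparison could then show fewer SAEs on plasma, or no difference, while the product adds serious reactions. The primary safety question would be answered with a mixture of the two effects.

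**Working it through.** **Inputs from the documents.** 100 plasma and 50 control (Section 3.1); shift odds ratio 2 (Section 3.3). Categories 4-7 in Table 2 sum to 10+10+5+5 = 30% v 7+6+3+2 = 18% in Scenario 1, and to 4+4+2+2 = 12% v 2+2+1+1 = 6% in Scenario 2.

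**Assumptions.** Fisher two-sided at 0.05. Table 2 gives Day 28 status, used here as a proxy for SAE incidence. Product-caused SAEs occur independently of the COVID-19 outcome, at illustrative rates *h* that are not in the documents.

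**The plan's own figure.** The only power stated is for the go decision, 74% and 80%. Simulating the tie-corrected (stratified) Mann-Whitney test at one-sided 0.15 with the Table 2 distributions gives 74.1-74.2% and 80.6-81.2%. The efficacy figures reproduce. No power or precision is stated for safety.

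**1. Precision of the difference.** Half-width = 1.96 × √[p(1−p)(1/100 + 1/50)].
- p = 5%: 7.4 points
- p = 10%: 1.96 × √(0.09 × 0.03) = 10.2 points
- p = 18%: 13.0 points

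The Newcombe interval at 10/100 v 5/50 is −12.2 to +9.3 points, and at 30/100 v 15/50 it is −16.0 to +14.5.

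**2. Fisher test with no overlap problem (exact enumeration).** Power to find plasma worse is 31% for 20% v 10% and 10.5% for 10% v 5%. With no control events, 9 plasma events are needed for P < 0.05 (8 v 0 gives 0.052).

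**3. What sameness would need.** Take an illustrative margin of 10 points, one-sided 0.025 and 80% power, with control n = (1.96 + 0.84)² × p(1−p) × 1.5 / 0.10². At 12% that is 125 controls, or 375 in total; at 30% it is 248, or 744 in total. At 100 v 50 the power is 43% and 24%.

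**4. Overlap with efficacy.** The plasma all-SAE rate is 1 − (1−d)(1−h), where d is the plasma rate of categories 4-7. Scenario 1 uses the exact odds-ratio-2 value, d = (0.30/0.70 ÷ 2)/(1 + 0.30/0.70 ÷ 2) = 17.65%; Scenario 2 uses the tabled 6%.

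| | h | Plasma v control | Plasma observed higher | Fisher: plasma worse |
|---|---|---|---|---|
| Scenario 1 | 5% | 21.8% v 30% | 13% | 0.1% |
| Scenario 1 | 10% | 25.9% v 30% | 28% | 0.5% |
| Scenario 2 | 5% | 10.7% v 12% | 38% | 0.9% |
| Scenario 2 | 10% | 15.4% v 12% | 70% | 6.1% |

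Swapping the convention changes little: tabled 18% in Scenario 1 with h = 5% gives 22.1% and 14%; the exact odds-ratio value in Scenario 2 (6.4%) gives 11.1% and 41%. With the tabled rates, product harm would have to reach 1 − 0.70/0.82 = 14.6% (Scenario 1) or 1 − 0.88/0.94 = 6.4% (Scenario 2) of plasma recipients just to equalise the all-SAE rates.

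**5. What a split buys.** If events other than COVID-19 progression run at 5% v an assumed 1%, plasma is observed higher in 92% of trials, but Fisher is significant in only 3.9%. At 10% v 0% Fisher is significant in 68%.

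**The case against.** A reader might infer that efficacy hides product harm altogether. The documents do not support that. Section 3.2 summarises SAEs by grade and type, and does not say the Fisher test is confined to the total, so a distinct reaction such as TRALI or anaphylaxis should be visible in the type table. Section 6.7 records an associated or not associated call for adverse events. Section 7.3 has halting rules for events associated with the product, and DSMB review of mechanical ventilation by arm because of antibody-mediated enhancement. Section 7.1 adds quarterly DSMB review.

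These points stand, with limits. The association call is not used in the Section 3.2 analysis, and it requires that no other etiology explain the event, so enhanced COVID-19 could be rated not associated. Type labels do not always separate product from disease: dyspnea and hypoxemia are listed among infusion reactions (Sections 2.5 and 7.3), and COVID-19 can produce them too. Halting rules and DSMB review protect participants during the trial; they do not supply the final between-arm estimate.

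A reader might also infer that the trial is committed to showing equivalence, or will read a non-significant result as no difference. Neither is stated. The sameness wording is in the monitoring section, not in the formal objective, and no rule for interpreting the Fisher test is given. What remains is an undertaking in Section 6.6 that the planned method cannot meet.

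Finally, the masking requires plasma to work, the product-harm rates are assumed, and Scenario 1 is the more unfavourable of the two extremes. Section 3.2 also promises a final SAP before unblinding, which may settle these points but is not among the documents.

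**Conclusion.** The concern holds in a limited form. Section 3.2 specifies no between-arm risk difference with an interval, and the sameness wording in Section 6.6 has no criterion that 100 v 50 could meet without a margin. That part does not depend on efficacy.

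Any pooled SAE comparison mixes efficacy with harm. Under the plan's own effect size and an assumed 5% of product SAEs, plasma would show the higher observed rate in only 13% (Scenario 1) to 38% (Scenario 2) of trials. At 10% assumed harm the range is 28% to 70%, so the size depends strongly on the scenario. The Day 28 proxy is imperfect: cumulative admissions are probably higher, while participants already in hospital at entry (inclusion criterion 4) add an SAE only if their stay is prolonged or another criterion is met.

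Harm is obscured in the pooled comparison rather than concealed from the trial. The grade 3 and 4 endpoint is a further gap, since Section 3.2 gives it no analysis. All of this can be settled in the final SAP and is worth settling there.

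**What to change.** 1. For both primary safety endpoints (SAEs, and grade 3 and 4 adverse events), report the between-arm risk difference with a two-sided 95% confidence interval, for example Newcombe or Miettinen-Nurminen. State the level, sidedness and unit of the Fisher test if it is kept.
2. Keep the all-SAE comparison, because antibody-mediated enhancement would appear there as progression. Beside it, add a prespecified split, classified blind to arm, into COVID-19 progression and other events, with infusion and transfusion-type events listed.
3. In Section 6.6, delete the claim to determine that risks are the same, or state a margin. Say in the SAP that a non-significant Fisher test will not be read as no difference.

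The cost is one blinded site classification on the SAE form, a few more tables and some SAP wording. The classification needs judgement and will sometimes be wrong. The split makes the result easier to interpret but does not by itself give the power to establish a small hazard (about 4% for 5% v 1%), and the report should say so.

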### 3.3 Power Consideration

Assuming a shift odds ratio of 2 under a proportional odds model on the severity rating scale, with a sample size of 150, the study will have 74% to 80% power of reaching the go decision in the scenarios we considered. The actual power will depend the distribution of the severity scale in the control arm. Table 2 gives the power of the two extreme scenarios: Scenario 1 describes scenario with higher rates for more severe outcomes, and Scenario 2 with majority of participants remaining or becoming PCR negative; the outcome distributions are identical between the two strata in these scenarios. We have evaluated the power for in-between scenarios and scenarios where non-infected and infected strata are different; the power is within the range 74% and 80% in all scenarios we have considered.

**Table 2: Power Calculation & Distribution of severity rating scale in the study**

Category	Scenario 1		Scenario 2	
	Control (albumin 5%)	Immune plasma	Control (albumin 5%)	Immune plasma
PCR negative	0%	0%	60%	75%
PCR positive, asymptomatic	0%	0%	0%	0%
PCR positive with symptom	70%	82%	28%	19%
Hospitalization	10%	7%	4%	2%
Hospitalization requiring oxygen	10%	6%	4%	2%
ICU/ventilation	5%	3%	2%	1%
Death	5%	2%	2%	1%
Study power	74%		80%	

## 4 STUDY PROCEDURES

### 4.1 Day -1 to 0 (Recruitment Pre Screen)

1. Script information about study protocol
2. Verification that the potential subject has interest in the study and is willing to attend a screening visit at the site on the next day
3. Verification that the potential subject had significant close contact with the COVID-19 case within the prior seven days OR has self-reported or documented recent evidence of infection by nasal swab (ID NOW or PCR) that is positive for SARS-CoV-2

#### 4. Medical eligibility questionnaire

- Ascertainment that the potential subject has risks for severe COVID-19 disease based on CDC risk criteria-age of the potential subject and their medical co-morbidities (hypertension, cardiovascular disease, pulmonary disease [including COPD or moderate to severe asthma], other immune suppressing condition)
- Verification that the potential subject is currently asymptomatic or minimally or moderately symptomatic of COVID-19 disease for  $\leq 7$  days

### 4.2 Day -1 to 0 (Screening Visit+)

1. Informed consent (obtained before performing study related activities) and assignment of screening PTID
2. New York Presbyterian Hospital (NYPH) blood transfusion consent (this is the standard procedure for all transfusions of blood products at NYPH)
3. Verification of eligibility (inclusion/exclusion)
4. Locator form
5. Demographics (age, sex ethnicity, race)
6. Medical history (timing of exposure to COVID---19 source patient, acute and chronic medical condition, medications, allergies. Any medical condition arising after randomization and infusion of study product should be recorded as AE)
7. COVID---19 symptom screen (fevers, cough, rhinorrhea, sore throat, diarrhea, shortness of breath, ADLs)
8. Vital signs (pulse, blood pressure, weight, height, temperature, oxygen saturation)
9. Targeted physical examination
10. ID NOW COVID-19 and PCR test to confirm positivity for SARS-CoV-2
11. Laboratory Evaluation
  - SARS-CoV-2 testing (RT-PCR) from nasal swab (10% of the swabs will also be submitted for viral culture).
  - ABO Blood typing (two tubes), CBC, comprehensive metabolic panel
  - Serological testing: anti-SARS CoV-2 titers
  - Blood samples for future studies, including sample for peripheral blood mononuclear cells
  - Urine or serum pregnancy test for females of childbearing potential.

---

 At screening, two swabs will be collected from each participant, one for ID NOW (or comparable rapid antigen test) and one for a PCR-based test. If ID NOW is positive, it will not be necessary to wait for the PCR based test result to confirm the positive. If the ID NOW is negative, it will be necessary to wait for the PCR test result: PCR negative will mean individual is not eligible and PCR positive will mean they are potentially eligible if all the other inclusion criteria are met.

Results from laboratory tests obtained up to 7 days before enrollment may be used for the pregnancy test.

- Volume overload
  - Volume status will be assessed via (1) medical history: history of congestive heart failure and use of heart failure medications; and (2) physical exam: vital signs, lung exam, assessment for peripheral edema.
  - Enrollment will be deferred for patients who have active volume overload in order to avoid cardiovascular decompensation from the receipt of additional volume. Once the patient's volume status has improved, enrollment may then proceed. [note this is not an exclusion]
  - For these patients, the potential risk of a recurrence of volume overload will be mitigated by infusing the plasma or albumin (a total of 400-500 mL) more slowly, i.e., over 2 - 4 hours.

### **4.3 Day 0 + Baseline**

1. Subjects will be contacted and scheduled for an infusion window
2. Randomization will then be done using an interactive web-based system to receive study convalescent plasma (CP) versus control (albumin 5%) at a 2:1 ratio
3. Study Product Administration: Two units of immune plasma or control (albumin 5%) will be transfused. Time at start and end of infusion will be recorded and vital signs will be measured immediately prior to infusion, 10-20 minutes after start of infusion, at completion of infusion and between 15-60 minutes after the end of the infusion.
4. COVID-19 symptom screen (fevers, cough, shortness of breath)
5. Assessment of clinical status (composite outcome of disease severity)
6. New medical conditions, concomitant medication, AE evaluation
7. Physical examination
8. SARS-CoV-2 testing (RT-PCR) from nasal samples

For follow-up visits, home visits by qualified phlebotomists and/or visiting nurses will be permitted.

### **4.4 Day 1**

1. COVID-19 symptom screen (fevers, cough, shortness of breath)
2. Assessment of clinical status (composite outcome of disease severity)
3. New medical conditions, AE evaluation

### **4.5 Day 3 ± 2**

1. Vital signs

2. COVID-19 symptom screen (fevers, cough, shortness of breath)
3. Assessment of clinical status (composite outcome of disease severity)
4. New medical conditions, AE evaluation
5. SARS-CoV-2 testing (RT-PCR) from nasal samples
6. Serological testing: anti-SARS-CoV-2 titers
7. Stored samples for future studies

#### **4.6 Day 7 ± 1**

1. Vital signs
2. COVID-19 symptom screen (fevers, cough, shortness of breath)
3. Assessment of clinical status (composite outcome of disease severity)
4. New medical conditions, AE evaluation
5. Targeted physical examination
6. SARS-CoV-2 testing (RT-PCR) from nasal samples
7. Serological testing: anti-SARS-CoV-2 titers
8. Comprehensive metabolic panel and CBC
9. Stored samples for future studies

#### **4.7 Day 14 ± 3**

1. COVID-19 symptom screen (fevers, cough, shortness of breath)
2. Assessment of clinical status (composite outcome of disease severity)
3. New medical conditions, AE evaluation
4. Targeted physical examination
5. CBC, comprehensive metabolic panel
6. SARS-CoV-2 testing (RT-PCR) from nasal samples
7. Serological testing: anti-SARS-CoV-2 titers
8. Stored samples for future studies

#### **4.8 Day 28 ± 7**

1. COVID-19 symptom screen (fevers, cough, shortness of breath)
2. Assessment of clinical status (composite outcome of disease severity)
3. New medical conditions, AE evaluation
4. SARS-CoV-2 testing (RT-PCR) from nasal samples
5. Serological testing: anti-SARS-CoV-2 titers
6. Stored samples for future studies

#### **4.9 Day 60 ± 7**

1. COVID-19 symptom screen (fevers, cough, shortness of breath)
2. Assessment of clinical status (composite outcome of disease severity)

3. New medical conditions, AE evaluation

#### **4.10 Day 90 ± 7**

1. Serological testing: anti-SARS-CoV-2 titers

+ In order to minimize exposure to SARS-CoV-2 virus, at the clinician's discretion, face to face interactions may be minimized by collecting information by phone or by telemedicine (Zoom HIPAA compliant conferencing)

### **5 EFFICACY, VIROLOGIC AND PK MEASURES**

#### **5.1 Clinical Efficacy (composite outcome of disease severity)**

1. Not hospitalized, negative PCR for SARS-CoV-2
2. Not hospitalized, positive PCR for SARS-CoV-2 without symptom
3. Not hospitalized, positive PCR for SARS-CoV-2 with symptoms
4. Non-ICU hospitalization, not requiring supplemental oxygen
5. Non-ICU hospitalization, requiring supplemental oxygen
6. Requiring mechanical ventilation and/or in ICU
7. Deceased

#### **5.2 Virologic measures**

- Rates and duration of SARS-CoV-2 PCR positivity (RT PCR) at days 0, 3, 7, 14 and 28
- Peak quantity levels of SARS-CoV-2 RNA at days 0, 3, 7, 14 and 28
- Culture positivity at baseline and at day 7 in a subset of specimens
- Correlation between viral culture positivity and PCR positivity for SARS-CoV-2

#### **5.3 Serologic titers**

- Serologic measures: Anti-SARS-CoV-2 titers at days 3, 7, 14, 28 and 90 days after infusion.

### **6 RISKS AND BENEFITS**

#### **6.1 Potential benefits of treatment**

The potential benefits of antiviral treatment with anti-SARS CoV-2 plasma in patients at high risk for developing COVID-19 due to a close contact with another individual with COVID-19 are unknown. However, it is anticipated that treatment will decrease the risk of developing symptomatic disease and decrease the severity of illness should it develop.

## **6.2 Potential risks of study procedures**

1. Risks of plasma: Fever, chills, rash, headache, serious allergic reactions, TRALI, TACO, transmission of infectious agents
2. Risk of albumin: chills, fever, low blood pressure, fast heart rate, urticaria, skin rash, nausea, TACO
3. Risks of phlebotomy: local discomfort, bruising, hematoma, bleeding, fainting
4. Total blood draws will not exceed 125 mL over the 90-day follow up period
5. Risks of nasal swab: local discomfort, vomiting
6. Risks of IV placement: bleeding, infection, thrombosis

